4.1 Background

Patients with short bowel syndrome (SBS) are characterized by reduced intestinal absorptive surface area due to extensive surgical bowel resection or congenital diseases, such as recurrent Crohn's disease or mesenteric vascular disease^{1,2,3,4}, resulting in decreased absorptive capacity of the gut.⁵ This causes a reduced uptake of nutrients, fluids, electrolytes, vitamins, and trace elements, leading to difficulties with maintaining metabolic balances when receiving a conventional diet.⁶ The malabsorption can lead to dehydration, malnutrition, and weight loss if left untreated.⁷

Whereas less severely affected SBS patients are able to compensate for their malabsorption by increasing oral intake (hyperphagia) and adapt metabolically or pharmacologically, more severely affected patients depend upon the safe and well-adjusted provision of parenteral support of nutrients, fluids, electrolytes, vitamins, and trace elements to maintain body function, growth, homeostasis, and health.⁸ For those dependent on parenteral support (PS), it is life-sustaining but at the same time associated with life-threatening complications. Among those are blood stream infections or sepsis,⁹ central vein thrombosis, liver damage¹⁰, and renal impairment.¹¹ In addition, the treatment burden of parenteral support is substantial. Often 10-18 liters of parenteral support per week are required. In addition to 10- to 12-hour over-night parenteral support infusions in such patients, additional hours during daytime may be required to compensate for losses. While liberating patients during daytime, night-time infusions disturb sleep and exacerbate the need for nocturnal urination. Adding to the treatment burden, patients on parenteral support often need frequent follow-up checks at the hospital, and for many there is a need for help from a homecare nurse.

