If endpoint not set to missing and no. of PS entry days \neq 7, missing PS entry days will be imputed with	0	Average of non-missing days	0	0	Tipping (from 0 to 1 by 0.1)*Average of non- missing days
Flexible window for endpoint assessment	7 consecutive days within the period between 1 and 14 days preceding visit date (30 days for baseline)	7 consecutive days preceding visit date	7 consecutive days within the period between 1 and 14 days preceding visit date (30 days for baseline)	7 consecutive days within the period between 1 and 14 days preceding visit date (30 days for baseline)	7 consecutive days preceding visit date
Allow window for endpoint assessment to cross previous visit	No (with exemption of Week 1 and 2)	Yes	No (with exemption of Week 1 and 2)	No (with exemption of Week 1 and 2)	Yes
Information from NTFs used	Yes	No	No	Yes	No

Abbreviations: PS: parenteral support, NTF = note-to-file

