• Difference between mean change from baseline in actual weekly PS volume at 12 weeks in the SBS population regardless of whether treatment is discontinued.

Supplementary 'hypothetical' estimand for the third key secondary efficacy endpoint

• Difference between mean change from baseline in actual weekly PS volume at 12 weeks in the SBS population, as if treatment discontinuation never occurred.

Fourth key secondary efficacy endpoint: Reduction in weekly PS volume of 100% (weaned off) at Week 24

The same estimands (main estimators) and sensitivity estimator will be investigated, as for the first key secondary efficacy endpoint (see Table 6). The same analysis method will be applied as well.

Primary 'composite' estimand for the fourth key secondary efficacy endpoint

25 August 2022

• Difference in percentage of reduction in weekly PS volume of 100% (weaned off) at Week 24 without treatment discontinuation between glepaglutide treatment group and placebo in the SBS population.

Supplementary 'treatment policy' estimand for the fourth key secondary efficacy endpoint

• Difference in percentage of reduction in weekly PS volume of 100% (weaned off) at Week 24 between glepaglutide treatment group and placebo in the SBS population, regardless of whether treatment is discontinued.

Note, the main analyses of the primary estimands follow the treatment policy strategy for the primary and third key secondary endpoints and the composite strategy for the first, second and forth key secondary endpoint. This is according to the confirmatory testing strategy described in the protocol version 10.0.

Table 6 Overview of estimands and handling of missing data for binary key secondary efficacy endpoints

Intercurrent event	Data observed or missing	Primary estimand 'Composite'		Supplementary estimand 'Treatment policy'
		Main estimator	Sensitivity estimator – PS vol derived based on 14-day period	Main estimator
Prematurely discontinuation of IMP	Observed	Non-response	Non-response	Value used as observed
	Missing	Non-response	Non-response	Response status derived from MI (CR Placebo)*
No prematurely discontinuation of IMP	Observed	Value used as observed	Value used as observed	Value used as observed
	Missing	Non-response	Non-response	Response status derived from MI (CR Placebo)*

Abbreviations: MI = multiple imputation, CR = copy reference

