Reduction of at least 30% in actual weekly PS volume from baseline to both Weeks 20 and 24

The difference in response in reduction of $\geq 30\%$ in PS volume from baseline to both Weeks 20 and 24 between each glepaglutide treatment group comparison to placebo will be tested using the CMH test adjusted for the stratification factor will be analyzed in a similar manner as the clinical response endpoint (first key secondary endpoint).

Reduction in prescribed weekly PS volume of 100% (weaned off) at Week 24

The difference in response in prescribed weekly PS volume of 100% (weaned off) at Week 24 between each glepaglutide treatment group comparison to placebo will be tested using the CMH test adjusted for the stratification factor will be analyzed in a similar manner as the weaned off endpoint based on actual PS volume (fourth key secondary endpoint).

PGIC improvement at weeks 4, 12, 20, and 24

PGIC improvement is defined as responding "Very Much Improved" or "Much Improved" on a 7-point Likert Scale for each of the weeks 4, 12, 20, and 24. Improvement between each glepaglutide treatment regimen compared to placebo will be tested by week, using the CMH test adjusted for the stratification factor. In similar fashion, improvement between each glepaglutide treatment regimen versus placebo will be tested using collapsed categories of Improvement, No Change, and Worsening, where Improvement is defined as a response of "Very Much Improved" or "Much Improved" or "Minimally Improved", and No Change is defined as the response of "No Change", and Worsening is defined as a response of "Minimally Worse" or "Much Worse" or "Very Much Worse". Improvement using collapsed 25 August 2022 Confidential Page 24 of 65

categories between each glepaglutide treatment regimen compared to placebo will tested by week using a Mantel-Haenszel chi-squared test for ordered categories. No imputation for missing values will be performed.

Change in weight from baseline to Week 24

The change in body weight (kg) from baseline to Week 24 will be presented descriptively by baseline BMI subgroup. Descriptive statistics will include the number of non-missing observations, mean, SD, median, minimum, and maximum values. A shift table by BMI subgroup from baseline to Week 24 will be presented. The BMI subgroups are defined as: <18.5 kg/m2, \geq 18.5 to <25 kg/m2, \geq 25 to <30 kg/m2 and \geq 30 kg/m2.

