APPENDIX A. CALCULATION OF PRESCRIBED AND ACTUAL WEEKLY PS VOLUME

Prescribed weekly PS volume based on a 7-day period

The prescribed weekly PS volume (L/week) record per patient per nominal visit attended on or after Visit 1 (Day 1) will be calculated. The source is the prescribed PS volumes recorded in the eCRF by the investigator (SDTM.CM where CM.CMSCAT= 'PARENTERAL SUPPORT PRESCRIPTION').

A prescribed PS regimen consists of \geq 1'bag identifier(s)' (SDTM.CM.CMSPID). For each prescribed 'bag identifier' the volume (SDTM.CM.CMDOSE) is recorded in L/week. The prescription of a 'bag identifier' is considered current from the start date (CM.CMSDTC) until the end date (CM.CMENDTC) or until the end of trial if the last prescription end date is not available, hereafter referred to as a prescription period.

A prescription period might cover several visits. A PS prescription can be updated at the scheduled visits, but also in between visits at the discretion of the investigator.

If the end date of a current prescription period is the same as the start date of the next prescription period, the end date of the current period is set to the end date minus one day to avoid overlap.

The prescribed volume (AVAL) is derived as the sum of the prescribed volumes during the 7day period just prior to the visit divided by 7 (to account for the volumes being recorded in L/week), i.e. the period is defined from the visit date minus 1 to the visit date minus 7. Hereafter referred to as the *prescribed volume*.

Note that, if the last PS prescription during the treatment period has been stopped more than 7 days prior to a visit, the prescribed weekly PS volume will be set to zero at the relevant visit.

Actual weekly PS volume based on a valid 7-day period

An actual weekly PS volume (L/week) record per patient per nominal visit attended on or after Visit 1 (Day 1) will be derived, with the exception of visits Day 3 and Week 1 which will not be included in the ADaM dataset (see steps below).

The source is the actual PS volume records entered into the eDiary by the patient (SDTM.ZP), hereafter referred to as volume records.

The actual weekly PS volume (AVAL) is derived as the sum of the volume records (ZP.ZPSTRESN) in a valid 7-day period prior to the relevant visit. Hereafter referred to as the *actual volume*.

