The weekly PS volume accounted for is derived as the actual volume in a valid 7-day period prior to the relevant visit plus prescribed volumes documented not taken (via notes to file) during the same period. Hereafter referred to as the *volume accounted for*.

The relevant prescribed volume is derived as the sum of the prescribed volumes during the valid 7-day period divided by 7 (to account for the volumes being recorded in L/week). Hereafter referred to as the *relevant prescribed volume*.

The steps to select a valid 7-day period and derive AVAL related to an attended visit are as follows:

- 1. The first period considered will be the 7-days period from the visit date minus 1 day to the visit date minus 7 days.
- 2. A valid period cannot start before the previous visit for post-baseline visits (before the last optimization visit for baseline visits). If the considered period starts before the previous visit date then, AVAL will be set to missing, ANLxxFL is set to ' ' and ANLxxREA = "Period starts before previous visit" and the loop stops.

Note that, the exemption to this rule will be that a Week 1 valid period will be allowed to start prior to the date of visit Day 3 (which is not included in the dataset) or baseline visit, and Week 2 valid period will be allowed to start prior to the dates of visits Week 1 or Day 3 (which is not included in the dataset).

- 3. Else, if there is at least one volume accounted for at each day in the eDiary for the period, then the period is considered valid, AVAL is derived as specified above, and ANLxxFL is set to 'Y' and the loop stops.
- 4. Else, if for the period, the volume accounted for is ≥ 90% of the relevant prescribed volume, then the period is considered valid, AVAL is derived as specified above, and ANLxxFL is set to 'Y' and the loop stops.

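### A Week 24 window with no infused volume, made valid by notes to file, counts as weaned off in the confirmatory fourth key secondary endpoint while PS is still prescribed

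*SAP*

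**What the plan says.** SAP Appendix A uses three quantities.

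- The analysed value: "The actual weekly PS volume (AVAL) is derived as the sum of the volume records (ZP.ZPSTRESN) in a valid 7-day period". Only infused volume enters it. Table 5 (SAP 3.1.4) confirms that, for the main estimator, days without an entry in a usable window contribute 0 L.
- The volume accounted for: the analysed volume "plus prescribed volumes documented not taken (via notes to file) during the same period". It serves only to judge whether the window is usable.
- The relevant prescribed volume: what was prescribed over the same window.

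The search begins with the seven days just before the visit. A window is accepted if every day is accounted for (step 3), or under step 4: "Else, if for the period, the volume accounted for is ≥ 90% of the relevant prescribed volume, then the period is considered valid". Acceptance ends the search. Otherwise the window moves back one day at a time, at most to days -8 to -14 for a post-baseline visit. If nothing qualifies, the value is missing.

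SAP 3.2 bases all key secondary endpoints on actual PS. The primary estimand of the fourth is "Difference in percentage of reduction in weekly PS volume of 100% (weaned off) at Week 24 without treatment discontinuation". Under Table 6, only stopping trial drug or missing data forces a non-response. SAP 3.4 adds "Reduction in prescribed weekly PS volume of 100% (weaned off) at Week 24" as a secondary endpoint without type I error control.

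**The concern.** Weaned off, in ordinary use, means that PS is no longer needed. Appendix A has another route to 0 L, which applies when no PS is prescribed in the days before the visit. That route fits the label. The note-to-file route has no such condition, and nothing in SAP 3.2 supplies one.

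Interruptions of PS are foreseeable in this population. Protocol 4.1 describes the complications of PS: "Among those are blood stream infections or sepsis". Exclusion criterion 1 gives catheter-related sepsis as an example of a reason for admission. The documents do not say why infusions come to be documented as not taken, so a link to such events is a possibility and not a finding.

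At stake is the meaning of a confirmatory endpoint. A week in which prescribed PS was not given can score as the best possible outcome. Unlike clinical response, which must hold at Weeks 20 and 24, this endpoint rests on Week 24 alone.

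**Working it through.** The plan gives no expected weaned-off rate, so there is no figure of its own to reproduce here. The sample-size table concerns the primary endpoint and does not enter.

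**Step 1: apply the rules.** Take an assumed patient prescribed 10 L/week.

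Accounted for (%) = (infused + documented not taken) / relevant prescribed × 100. Analysed value = infused volume, if the window is valid.

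| Days -1 to -7 | Accounted for | Window | Value | Weaned off? |
|---|---|---|---|---|
| 10 L documented not taken | (0+10)/10 = 100% | valid, search stops | 0 L | yes |
| 9 L documented not taken, 1 L without record | (0+9)/10 = 90% | valid, search stops | 0 L | yes |
| 8 L documented not taken, 2 L without record | (0+8)/10 = 80% | not valid, search moves back | – | not from this window |
| 8 L documented not taken, 2 L infused | (2+8)/10 = 100% | valid, search stops | 2 L | no |
| 10 L not infused, no notes | 0/10 = 0% | not valid, search moves back | – | not from this window |

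The first two rows give a 100% reduction with 10 L/week still prescribed. The fourth shows that one recorded infusion is enough to prevent it. The last shows what the notes do: without them the search goes back as far as day -14, and finding no valid window gives a missing value, hence non-response.

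**Step 2: check the planned safeguards.**

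- The 14-day sensitivity derivation in Table 6 applies to this endpoint. One normal and one skipped week give (10 + 0)/2 = 5 L/week, not weaned off. Two skipped and documented weeks still give 0.
- The prescription-based endpoint in SAP 3.4 would count the same patient as not weaned off, so the two analyses would disagree visibly.
- Supportive estimator 2, which drops notes to file, is planned only for the primary endpoint (SAP 3.1.4).
- Raising the threshold to 95% (supportive estimator 3, also primary endpoint only) leaves the first row unchanged, since 100% is accounted for.

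None of these alters the confirmatory test.

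**Step 3: size.** With 36 per arm (Protocol 7.1), one patient is 1/36 = 2.8 percentage points. For a single-table Cochran-Mantel-Haenszel test with a and b responders, n = 36 per arm, N = 72 and r = a + b:

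expected E = r/2; variance V = n²·r·(N − r) / [N²(N − 1)]; χ² = (a − E)²/V on 1 df.

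| Assumed responders, active vs placebo | E | V | χ² | p |
|---|---|---|---|---|
| 5 vs 0 | 2.5 | 1.180 | 5.30 | 0.021 |
| 5 vs 1 | 3.0 | 1.394 | 2.87 | 0.090 |
| 6 vs 1 | 3.5 | 1.602 | 3.90 | 0.048 |

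One misclassified placebo patient turns 0.021 into 0.090. One on active turns 0.090 into 0.048. The comparison is with 0.05 because SAP 3.3 tests the last two key secondary endpoints at the full α. The counts are assumptions; the stratified test would differ somewhat.

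**The case against.** The strongest reply is that the rule does what it says. The endpoint is defined on actual volume, and 0 L is the true actual volume for that week. The sponsor pre-specified both a 14-day derivation of this endpoint and a prescription-based companion, so the situation would be visible. This stands as far as it goes: the problem is the label and the missing prescription condition, and both checks deserve credit. They remain outside the confirmatory test.

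Second, the scenario is narrow. Every infusion must be absent for seven days, in patients who entered needing PS at least three days a week. Protocol 11.2.4 asks patients still on PS for a 48-hour measurement that includes a PS day within seven days of the visit, and Protocol 10.4 has visits rescheduled when diary data are lacking. These steps make the case rarer, but they do not bind the derivation.

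Third, the endpoint is last in the hierarchy. It is reached only after six hypotheses and the third key secondary endpoint have succeeded, so no other confirmatory claim depends on it. That is correct and limits the consequence.

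A reader might also infer that the note alone takes a patient from no reduction to a 100% reduction. That would need a valid earlier window with volume still at baseline. The documents guarantee neither, and even placebo is expected to fall by 2.3 L/week (SAP 2.6).

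**Conclusion.** The point holds as a consequence of the written rules. A patient with no infused volume in the selected Week 24 window, and with at least 90% of the prescribed volume or every day accounted for through notes to file, is a confirmatory weaned-off responder while PS is still prescribed.

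Each such patient moves an arm's rate by 2.8 points. With few responders, one can change the conclusion in either direction, but that rests on assumed counts, 36 per arm and an unstratified test. The documents give neither the frequency of such weeks nor their split between arms. A reader might infer a bias in favour of glepaglutide; nothing in the documents supports that.

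Nor does the point reach the primary endpoint. Its estimand is stated in terms of actual volume (SAP 2.3), and the derivation follows it. This is a definition that should be tightened before unblinding, not a flaw that undermines the trial's main result.

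**What to change.** In SAP 3.2, define the fourth key secondary endpoint as met only if the actual volume is 0 and the relevant prescribed volume in the same selected window is also 0. Otherwise count non-response. List patients with actual 0 and prescribed above 0 by arm.

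The cost is one extra condition on a variable that Appendix A already derives. A prescription without an end date is treated as current to the end of the trial, so a patient who has truly stopped PS but whose end date is late or missing could be scored as a non-responder. This is a small loss. With no entries and no notes, such a patient has 0% accounted for and the window already fails. The new condition matters only where the window is valid through notes to file or zero entries. Prescription end dates should therefore be queried before unblinding.

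The same week would still enter the primary analysis as 0 L. That difference is acceptable because the two endpoints ask different questions, but the SAP should say so. The change touches only the scoring of this endpoint, not the management of PS.

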8.7.4 Parenteral Support Volume Adjustments due to Clinical Signs

Especially in the beginning of the trial drug Treatment Phase, the Investigator must be in frequent contact with the patient. If the patient presents with clear adverse clinical signs of fluid overload, PS volume may be reduced without 48-hour urine measurements being available. During the next scheduled 48-hour measurement period however, further PS volume adjustments might have to be considered based on the results of the 48-hour urine measurement.

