9. CHANGES FROM PREVIOUS SAPS

SAP version	SAP section	Summary of change	Rationale for change
$5.0 \rightarrow 6.0$	General	• Editorial changes throughout e.g. document version, dates, table and figure references, addition/removal of sections, changes to header titles etc.	• To have a coherent document
$5.0 \rightarrow 6.0$	1.1	Responsibility of TFL generation transferred to Zealand Pharma	• To reflect internal strategic decision
$5.0 \rightarrow 6.0$	2.3	Editorial changes	• To make the specification of primary estimand of primary endpoint clear
		• Addition of supplementary estimand	• To make the specification of supplementary estimand of primary endpoint clear
$5.0 \rightarrow 6.0$	3.1	• Introduction of terminology main estimator and sensitivity estimators	• For ease of reference
		 Addition two sensitivity analyses Tipping point analysis Analysis on all observed data 	• To further explore robustness of primary analysis of primary endpoint in terms of missing data assumptions under which the conclusions change and impact of using multiple imputation methods, respectively
		• Addition of Table 3	• To provide a better overview of the various estimands and estimators, and how missing data is handled
		• Addition of Week 1 to the primary analysis model	• To accurately determine the study drug's treatment effect in the early weeks
$5.0 \rightarrow 6.0$	3.1.1	• New section divider added	• For ease of navigation
		• Definition of collapsing PGIC groups redefined	• Collapsing of groups is now made based on current data distribution to

SAP version	SAP section	Summary of change	Rationale for change
		• Spearman rank-order and Kendall's tau-b correlation coefficients added	 support interpretation in the best possible way To further specify the type of correlation coefficients used. The coefficients are chosen based on their typical use in psychometric evaluation of assessment tools
$5.0 \rightarrow 6.0$	3.1.2	New section divider added	For ease of navigation
$5.0 \rightarrow 6.0$	3.1.3	New section divider added	• For ease of navigation
$5.0 \rightarrow 6.0$	3.1.4	• New section introduced with addition of supportive analyses for primary endpoint derivation (actual weekly PS volume)	• To explore robustness of the primary statistical analysis with regard to the primary endpoint derivation

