If the loop is not stopped in steps 1, 2, 3 and 4 then a new 7-day period is defined from the visit date minus 2 days to visit date minus 8 days and the loop is re-started (steps 2, 3, and 4). For post-baseline visits, the loop can be re-started until the new 7-day period is from the visit date minus 8 days to the visit date minus 14 days. For baseline visits, the loop can be re-started until the new 7-day period is from the visit date minus 14 days. For baseline visits, the loop can be re-started until the new 7-day period is from the visit date minus 24 days to the visit date minus 30 days. If the loop reaches earliest allowed period without stopping then AVAL will be set to missing, ANLxxFL =' ' and ANLxxREA = "No valid period identified".

Note that, if there are 7 days without relevant prescribed PS prior to a visit, then the period will be considered valid, AVAL will be derived as the sum of available volumes found in the 7-day prior to the visit, and the ANLxxFL will be set to 'Y'. If and there are no PS volume entries in the eDiary, AVAL will be set to 0 (zero).

Note: that for calculating \geq 90% volume accounted for, the relevant prescribed volume will be calculated using the same time-period as the actual volume, in contrast to the prescribed parameter described above, which strictly uses the values in the period visit date minus 1 day to visit date minus 7 days for the derivation.

Prescribed and actual weekly PS volume based on a 14-day period

The same rules as stipulated above apply when calculating the **actual** weekly PS volume based on a 14-day valid period, except that the loop can be re-started until the 14-day period is from the visit date minus 28 days to the visit date minus 15 days.

Note that, if the last prescription end date is more than 14 days prior to the visit, and there are no PS volume entries in the eDiary, the actual weekly PS volumes (AVAL) will be set to 0, and ANLxxFL will be set to 'Y'.

Note that, for the actual volumes the Day 3, Week 1 and Week 2 visits will not be included in the dataset, and hence the Week 4 valid 14-day period is allowed to start before the date of any of these visits.

The **prescribed** weekly PS volume will be derived as described above but based on the period from the visit date minus 1 to the visit date minus 14. Note that, if the last prescription end date is more than 14 days prior to the visit, the prescribed weekly PS volumes (AVAL) will be set to 0, and ANLxxFL will be set to 'Y'.

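### The Week 1 look-back in SAP Appendix A can reach the pre-dose baseline week, so a Week 1 change from baseline can be zero by construction

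*SAP*

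**What the plan says.** SAP Appendix A derives the actual weekly PS volume by searching backwards for a valid week. The starting point is the same for every visit: "The first period considered will be the 7-days period from the visit date minus 1 day to the visit date minus 7 days". A window is accepted if a volume is accounted for on every day (step 3) or, failing that, if at least 90% of the volume prescribed for those same days is accounted for (step 4). If neither holds, the window moves back one day. For post-baseline visits this can continue until "the new 7-day period is from the visit date minus 8 days to the visit date minus 14 days".

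Step 2 limits the search: "A valid period cannot start before the previous visit for post-baseline visits". Week 1 and Week 2 are exempted. A Week 2 window may cross the Week 1 and Day 3 visits. A Week 1 window goes further and is "allowed to start prior to the date of visit Day 3 (which is not included in the dataset) or baseline visit". Table 5 in SAP 3.1.4 repeats the search range for the main estimator, "7 consecutive days within the period between 1 and 14 days preceding visit date", and the exemption for Weeks 1 and 2.

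SAP 3.1 includes Week 1 in the primary MMRM, and SAP 5.3.1 includes it in the imputation model. SAP section 9 gives the reason for adding it as determining the drug's "treatment effect in the early weeks". However, SAP 5.3 still says that Week 1 is left out of the calculations, and the opening of the actual-volume part of Appendix A still says that it will not be in the analysis dataset.

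**The concern.** The exemption and the look-back limit each look reasonable alone. Together they allow a Week 1 value to be built from days before the first dose. Nothing in Appendix A requires a Week 1 window to contain a post-dose day or to differ from the window used for baseline. When the two windows coincide, a Week 1 value that could not be derived from treatment-period data is replaced by the baseline value, in any arm, and is analysed as an observed response of exactly zero. That works against the reason given for adding Week 1. The problem is specific to Week 1, because Week 2 is not exempted from the baseline visit.

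**Working it through.** **Inputs.** The Week 1 visit is Day 8 ± 2 (Protocol 10.4.3), so Day 6 to Day 10. The first window, the look-back limit and the exemption come from SAP Appendix A. Count days from the Visit 1 date as 0, so a visit on Day d falls at v = d − 1. Pre-dose means a calendar day before Visit 1.

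**Windows.** After s one-day shifts (s = 0 to 7) the Week 1 window runs from v − 7 − s to v − 1 − s.

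**Check against the plan's own figure.** The 8 candidate windows together cover 1 to 14 days before the visit, which matches Table 5.

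**Overlap with baseline.** The first baseline window is −7 to −1. A Week 1 window equals it when v − 7 − s = −7, that is, when s = v. Since s cannot exceed 7, this is possible for v = 5, 6 and 7 (Days 6, 7 and 8) and impossible for v = 8 and 9 (Days 9 and 10).

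| Week 1 visit | First window | Pre-dose days in it | Earliest window | Pre-dose days in it | Shift giving the first baseline window |
|---|---|---|---|---|---|
| Day 6 | −2 to +4 | 2 | −9 to −3 | 7 | 5 |
| Day 7 | −1 to +5 | 1 | −8 to −2 | 7 | 6 |
| Day 8 | 0 to +6 | 0 | −7 to −1 | 7 | 7 |
| Day 9 | +1 to +7 | 0 | −6 to 0 | 6 | none |
| Day 10 | +2 to +8 | 0 | −5 to +1 | 5 | none |

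**Illustration (assumed patient).** Take 2 L/day, 14 L/week prescribed, a complete diary up to Visit 1 and no entries from Visit 1 onward.

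- Baseline: window −7 to −1, 7 × 2 = 14 L.
- Day 8 visit: each window containing a blank day fails step 3. The best of them, −6 to 0, accounts for 6 × 2 = 12 L, and 12/14 = 86%, so it fails step 4 too. The next window, −7 to −1, has 14 L and is accepted. Week 1 = 14 L and change = 14 − 14 = 0. Day 6 and Day 7 visits reach the same window and the same result.
- Day 9 visit: the earliest window has 12/14 = 86%, so Week 1 is missing. Day 10: 10/14 = 71%, also missing.
- Entries on days +1, +3 and +5 only: the same results for all five visit days.
- Baseline-visit exemption removed: Week 1 is missing in every one of these cases.

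**Consequence of simply deleting the exemption.** The number of admissible windows for Days 6 to 10 would be 0, 0, 1, 2 and 3. Every Day 6 or Day 7 visit would lose its Week 1 value even with a complete diary, so plain deletion is too blunt.

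**The case against.** Several points on the other side stand and limit the finding.

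- **Both tests must fail.** A window below 90% is still accepted if every day is accounted for, and the loop stops at the first valid window. At a Day 8 visit, all seven later windows must fail before the pre-dose week is reached.
- **Early reductions are mostly kept.** Under Protocol 8.7.4, with clear signs of fluid overload, "PS volume may be reduced without 48-hour urine measurements being available". A reader might infer that the look-back routinely erases such reductions. The documents do not support that. The 90% test uses the prescription for the same days, and Appendix A allows prescriptions to change between visits, so a cut entered as a prescription lowers the denominator. Volumes documented as not taken in a note to file count as accounted for. Protocol 6.2 also requires the reason for between-visit changes in the eCRF. A reduction is lost only if it is neither prescribed nor in a note to file and days lack entries, or if there is a separate diary gap.
- **Little change is expected this early.** Algorithm-based adjustment starts at the Week 1 visit (Protocol 8.7.3), and the Week 1 value covers the week before it. Most true changes will be near zero. That limits the damage but does not make a pre-dose week a post-baseline observation.
- **Pre-dose days in the first window are not an Appendix A defect.** The 2 such days at a Day 6 visit, and 1 at Day 7, follow from the 7-day definition in Protocol 12.3.1 and the visit window.
- **Some supportive analyses avoid the look-back.** Supportive estimators 1 and 4 use the 7 days before the visit, and the 14-day sensitivity derivation drops Weeks 1 and 2. However, estimators 1 and 4 change other elements at the same time, and estimators 2 and 3 keep the exemption, so none isolates this element.
- **Two sentences say Week 1 is not derived at all.** Read literally they would remove the problem, but they contradict SAP 3.1, Table 5, the exemption itself and the change log. They look like leftover text.

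**Conclusion.** The rule is wrong as written, with low impact. For Week 1 visits on Days 6 to 8, including the nominal day, the accepted week can be wholly pre-dose and identical to the first baseline window. For Days 9 and 10 identity is impossible, but a back-shifted window can still hold up to 6 or 5 pre-dose days of 7. This rests on date arithmetic from the SAP text and on reading Week 1 as a derived visit.

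How often it would happen depends on diary gaps just after the first dose, which the documents do not quantify.

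A reader might infer that the primary Week 24 result is materially biased. The documents do not support that. No confirmatory endpoint is at Week 1. Week 1 acts on the Week 24 contrast only as one of eight repeated measures and as a predictor in the imputation. Once the data are imputed, the remaining route in an MMRM with unstructured covariance and visit-by-treatment terms is the baseline and stratum coefficients shared across visits. The effect should therefore be small; it was not simulated. The estimate most directly affected is the Week 1 contrast itself.

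**What to change.** In Appendix A, restrict the Week 1 exemption:

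1. Only the first window (visit minus 7 to visit minus 1), which is the protocol's own definition, may start before Visit 1.
2. A back-shifted Week 1 window may not start before Visit 1.
3. If no permitted window is valid, Week 1 is set to missing. Where later visits have values, the existing within-arm MAR step for intermittent missing data in SAP 5.3.1 imputes it.

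This leaves 1, 1, 1, 2 and 3 permitted windows for visits on Days 6 to 10, and at most 2 of 7 days can be pre-dose. Align Table 5, and correct the sentences in SAP 5.3 and at the start of the actual-volume part of Appendix A that say Week 1 is not derived.

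Scaling the 5 or 6 post-dose days of an early visit up to a week is not advised, because it distorts intermittent schedules. A stable patient infusing on days 1, 3 and 5 of the week (Protocol Table 4) has 2 or 3 infusions in any 5 days. Scaled by 7/5 that is 2.8 or 4.2 per week, an error of −7% or +40%. At 12 L/week it would record 11.2 or 16.8 L with no true change.

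The cost is a few lines of text and a few more missing Week 1 values.
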